5.1 Inclusion Criteria

In order to be included in the study, the following inclusion criteria will be used.

Inclusion Criteria:

- Provide implicit consent by filling out and submitting the survey.
- Used a Mosie Kit to conceive during at least one cycle.
- At least 18 years old.
- Has an active email on file (presumed or they would not have received an invitation to participate. This information will not be verified as there is a desire to keep the survey completely anonymous.)

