Analysis: Descriptive statistics surrounding the ease of use on a 5-point likert (very easy to very difficult) will be analyzed on five different aspects of use. Specifically, the steps of using the Mosie Kit (collecting a sperm sample, drawing up the sample in the Mosie syringe, inserting the syringe, and depositing the sperm at or near the cervix) and overall ease of use will be examined. Additionally questions related to use such as comfort, ease and safety of the process, enjoyable and intuitiveness of use (able to use it without instructions) will allow the user to rate their experience from Strongly agree to strongly disagree (5 point scale). The data will be plotted and examined as part of the analysis.

Secondary Hypothesis 2: The participants were able to use the Mosie Kit as instructed using the instructions contained in the kit. The alternative hypothesis is that the participants were not able to use the kit using the instructions contained in the kit.

Analysis: Descriptive analysis of perceived overall success rate will be analyzed. Additionally, descriptive analysis of the frequency of each expected behavior related to use of the kit will be examined.

Secondary Hypothesis 3: The participants reported they used the kit as intended, specifically, using it within 24 hours of initial signs of ovulation and again 24-48 hours after ovulation was confirmed or expected. The alternative hypothesis is that the participants report they did not use the kit as intended with respect to timing (within 24 hours of initial signs of ovulation and again 24-48 hours post ovulation).

Analysis: Frequency rates related to timing of insemination at all reported cycles will be analyzed. The data will be reported in both total number of attempts at each time point as well as percentage of attempts at each time point in comparison with total cycles where the Mosie Kit was used. T-tests will also be used in this analysis. Additionally,

amount of time lying after insemination and position of lying will be analysed using descriptive statistics and correlations with pregnancy rate.

Secondary Hypothesis 4: Participants reported they perceived the Mosie Kit to be a safe way to conceive. The alternative hypothesis is that participants did not perceive the Mosie Kit to be a safe way to conceive.

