Analysis: Descriptive statistics will be used to analyze perceived safety. Qualitative analysis will be used on any comments made related to safety. Rates of vaginal infections will be analyzed using descriptive statistics.

Secondary Hypothesis 5: The majority of participants indicate they have little to no safety concerns related to using the Mosie Kit. Alternative hypothesis is the majority of participants will be very concerned or extremely concerned about the safety of using the Mosie Kit.

Analysis: Descriptive statistics of self-reported level of concern. Additionally, safety measures such as hand washing, disposing of the syringe after use, and reading the instructions will be examined using descriptive statistics.

Tertiary Hypothesis 1: There will be higher pregnancy rates when using the Mosie Kit when the source of infertility is male-based than when it is female-based. The alternative hypothesis is there will be lower pregnancy rates when using the Mosie Kit when the source of infertility is male-based than when it is female-based.

Analysis: In addition to the descriptive statistics a t-test will be run to examine this hypothesis.

Tertiary Hypothesis 2: There is a difference in pregnancy rates of people with known fertility issues depending on the source of their infertility. Specifically, the following sources of infertility will be examined if sufficient data is available.

- o PCOS
- Endometriosis
- Low AMH or low ovarian reserve
- Low sperm count
- Sperm motility issues
- Unexplained infertility
- Erectile dysfunction
- Performance issues or sexual anxiety, or inability to orgasm with partner.

Page 27

- Vaginismus or vulvodynia
- Tilted uterus
- Multiple uterus/cervix
- Loss of a fallopian tube

The alternative hypothesis is that there will be no difference in the fertility rates associated with different sources of infertility.

Analysis: Descriptive statistics, t-test, correlations and multiple ANOVAs will be used to examine this hypothesis.

Tertiary Hypothesis 3: There will be a difference between individuals who perform 2 insemination instances as described in the instructions and those that follow a different schedule or dosage number. The alternate hypothesis is that there will be no difference between the individuals that perform the minimum 2 insemination instances and those that follow difference dosage schedule.

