[figure not shown]
How did you or your partner time your ovulation? (Select all that apply.) *
Count days in cycle
Track vaginal or cervical fluids
Tracking changes in the cervix
Use ovulation predictor kit
Use an app to estimate ovulation
Basal Body Temperature
Wearable device
Did not time ovulation
Did using Mosie result in a pregnancy? *
O Yes
O No
Back Next Page 10 of 20

[figure not shown]
Never submit passwords through Google Forms.

 $This \ content \ is \ neither \ created \ nor \ endorsed \ by \ Google. \ \underline{Report \ Abuse} - \underline{Terms \ of \ Service} - \underline{Privacy \ Policy}$

Google Forms

Page 56

[figure not shown]

Safe process

Enjoyable

	Very Easy	Easy	Neutral	Difficult	Very Difficult
To collect the semen/sperm sample in the cup?	0	0	0	0	0
To draw up the semen/sperm in the syringe?	0	0	0	0	0
Insert the Mosie syringe into the vagina up to the handles?	0	0	0	0	0
To deposit the semen/sperm at or near the cervix using the syringe?	0	0	0	0	0
My overall impression on the ease of use	0	0	0	0	0
					Page 12 of 20
submit passwords to	through Google Fo				

MOSIE-001 © 2020 Mosie Baby Page 59

MOSIE-001 © 2020 Mosie Baby

Page 60

Pulled the syringe plunger back and forth to confirm it was functioning.

My partner washed their hands

Use a sperm friendly-lubricant.

Thawed out donor sperm from sperm bank

Prepared all items and have them handy ready to use.

Washed the penis

that	apply)?*
	Lie down in a comfortable position.
	Relax
	Receive oral sex
	Stimulate clitoris
	Use any vibratory or non-vibratory stimulation device intravaginally
	Have an orgasm
	Other:
	erall, how well were you able to use the Mosie syringe to inseminate yourself our partner? * Very Able
	our partner? *
or y O O O	our partner? * Very Able Able Not Very Able
or y 0 0 0 0	Very Able Able Not Very Able Not Able at All Volume at All Volume at All Volume at All Volume at All Able at All Volume at All Able at All Able at All
or y O O O	Very Able Able Not Very Able Not Able at All Volong did you remain laying down after using the Mosie syringe? * Less than 15 minutes

Willelf best descri	ibes your lying position? *	
On my stomach	n	
On my side		
On my back		
On my back wit	th my hips elevated by a pillow	
Other:		
O No		
O		
What type of sam	ple did you use? *	
What type of sam	ople did you use? * rom a sperm bank (frozen)	
What type of sam	rom a sperm bank (frozen)	

0 2000	thank 50%	
O 51%-	70%	
O 71% -	80%	
O 81%-	90%	
O 90%-	95%	
O 96%-	100%	

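### Secondary Hypothesis 2 concerns using the kit from its own instructions, but neither planned analysis is restricted to or split by whether the respondent read them

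*Combined protocol and SAP*

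**What the plan says.** Section 9.1 states Secondary Hypothesis 2 as: "The participants were able to use the Mosie Kit as instructed using the instructions contained in the kit". The alternative given there is also about the instructions.

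The analysis has two sentences. The first is "Descriptive analysis of perceived overall success rate will be analyzed". The second adds that "descriptive analysis of the frequency of each expected behavior related to use of the kit will be examined". No denominator, success threshold or formal test is given for either.

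The plan does not name the survey item that supplies the overall success rate. The legible item in Appendix A that fits asks "how well were you able to use the Mosie syringe to inseminate yourself" or a partner, on a four-level scale from Very Able to Not Able at All. It does not mention instructions.

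Reading the instructions appears by name in the analysis of Secondary Hypothesis 5: "safety measures such as hand washing, disposing of the syringe after use, and reading the instructions will be examined using descriptive statistics". It is not linked to Secondary Hypothesis 2.

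Other sections point to an all-respondent denominator. The only kit-related inclusion criterion (section 5.1) is "Used a Mosie Kit to conceive during at least one cycle". Section 9.3 analyses the sample as a whole and by sex, age and type of relationship. Reading the instructions is not among the subgroup factors in section 9.4.2.

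**The concern.** The hypothesis has a condition in it: use by means of the supplied instructions. Neither analysis carries that condition. A respondent who never opened the instructions counts in the success rate exactly as one who followed them line by line, whether that respondent managed well or badly.

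The result has a use. Section 2.3.2 says the research will let the sponsor know whether it has communicated how to use the kit and whether the instructions need changing. Section 3 ties following the instructions to where the semen is deposited. Of the listed hypotheses, this one addresses the instructions most directly. If its reported percentage mixes two groups in an unknown proportion, a reader of the results cannot tell how the people who read the instructions fared.

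**Working it through.** **1. The plan's own precision.** Section 9.2 gives a 95% margin of 4.4 points at 500 completed surveys and 5 points at 384. The worst-case half-width is 1.96 × √(0.25/n).

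- n = 500: 0.0438, or 4.4 points.
- n = 384: 0.0500, or 5.0 points.

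Both reproduce. The documents give no figure specific to Secondary Hypothesis 2.

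**2. What pooling does.** Let q be the share who did not read the instructions, and let s_R and s_N be the success proportions in readers and non-readers.

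- Pooled success = (1 − q) × s_R + q × s_N.
- Pooled minus readers' success = q × (s_N − s_R).

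The sign is that of s_N − s_R. The difference is zero if q = 0 or if the two groups succeed equally.

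**3. Illustrations.** None of q, s_R or s_N is in the documents, so all values here are assumptions.

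| s_R | s_N | q | Pooled | Pooled minus readers |
|---|---|---|---|---|
| 80% | 97% | 10% | 0.9 × 80 + 0.1 × 97 = 81.7% | +1.7 points |
| 80% | 97% | 40% | 0.6 × 80 + 0.4 × 97 = 86.8% | +6.8 points |
| 80% | 63% | 10% | 0.9 × 80 + 0.1 × 63 = 78.3% | −1.7 points |
| 80% | 63% | 40% | 0.6 × 80 + 0.4 × 63 = 73.2% | −6.8 points |
| 50% | 95% | 10% | 0.9 × 50 + 0.1 × 95 = 54.5% | +4.5 points |
| 50% | 95% | 30% | 0.7 × 50 + 0.3 × 95 = 63.5% | +13.5 points |

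With a 17-point gap between the groups, the distortion reaches the planned 4.4-point margin when q = 4.4/17, about 26%. Below that share it lies inside the margin.

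**4. Precision if readers are the denominator.** With a reading share r, n falls to 500 × r, or 384 × r at the minimum sample. The values of r are assumptions.

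| r | n from 500 | Half-width | n from 384 | Half-width |
|---|---|---|---|---|
| 90% | 450 | 4.6 points | 346 | 5.3 points |
| 80% | 400 | 4.9 points | 307 | 5.6 points |
| 70% | 350 | 5.2 points | 269 | 6.0 points |
| 50% | 250 | 6.2 points | 192 | 7.1 points |

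**5. Whether the second analysis closes the gap.** The expected-behavior frequencies do bear on use as instructed, and reading could be one of the behaviors counted. As described, however, they are separate frequencies. A table showing that some percentage read the instructions and some percentage performed a step does not show what percentage of those who read performed it. Only the cross-tabulation does.

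**The case against.** The strongest reply is that Secondary Hypothesis 2 is already served by two analyses, and that the second, on step-by-step behavior, goes directly to use as instructed. Other planned evidence also bears on the instructions: ease ratings for each step (Secondary Hypothesis 1), timing against the instructed schedule (Secondary Hypothesis 3), the reading frequency itself (Secondary Hypothesis 5) and categorised open comments (section 9.4.1). Section 4.2 promises information on how easy the instructions are to use, and several survey pages are not shown, so a dedicated item may exist. The hypothesis speaks of the participants, so an all-respondent denominator is defensible, and failure to read may itself reflect poor communication.

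Much of this stands. It is why the all-respondent figures should stay, and why a reader should not infer that the study as a whole is unable to inform the sponsor about the instructions. It does not remove the gap: no planned analysis of this hypothesis is conditioned on reading, and its text names no item on instruction clarity.

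Three further inferences are tempting and unsupported:

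- **That pooling will generally flatter the instructions.** This needs non-readers to do better than readers, and nothing in the documents says so.
- **That the plan expects people to skip the instructions.** Under Secondary Hypothesis 1 it includes an agree-to-disagree rating of intuitiveness, described as being able to use the kit without instructions. That is a rating, not a forecast of behavior.
- **That a high pooled figure would confirm the hypothesis even if nobody had read the instructions.** The plan sets no decision rule here, and the reading frequency under Secondary Hypothesis 5 would expose that case.

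**Conclusion.** The hypothesis and its analysis do not match. The pooled percentages answer how all respondents fared, not how people who read the instructions fared. The distortion may run in either direction and its size is unknown. On the assumed 80% and 97% rates it is 1.7 to 6.8 points for 10% to 40% non-readers. A wider assumed gap enlarges it, and it vanishes if everyone read or if the groups succeed equally.

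The conclusion rests on two inferences. The denominator is taken to be all respondents because sections 5.1, 9.3 and 9.4.2 point that way. The legible ability item is taken to be the source of the overall success rate. Severity is minor: this is a descriptive secondary hypothesis, and the repair is cheap.

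**What to change.** In section 9.1, under Secondary Hypothesis 2:

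- Keep the all-respondent figures.
- Name the survey item used for overall success.
- Cross-tabulate that item, and the frequency of each expected behavior, by whether the respondent read the instructions, with 95% confidence intervals.
- State that the readers' column is the result that addresses this hypothesis, and report the share who read beside it.

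This is a wording change, provided a reading item is collected as the Secondary Hypothesis 5 analysis indicates. That item is not legible in the survey pages, so its presence and response options should be confirmed.

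The cost is precision: the half-widths in the check above apply to the readers' column, and the non-readers' column will be less precise still if few did not read. The readers' result also has a limit that should be stated in the report: it does not separate clear instructions from intuition or prior experience with similar devices.

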Secondary Hypothesis 2: The participants were able to use the Mosie Kit as instructed using the instructions contained in the kit.

Secondary Hypothesis 3: The participants reported they used the kit as intended, specifically, using it within 24 hours of initial signs of ovulation and again 24-48 hours after ovulation was confirmed or expected.

Secondary Hypothesis 4: Participants reported they perceived the Mosie Kit to be a safe way to conceive.

Secondary Hypothesis 5: The majority of participants indicate they have little to no safety concerns related to using the Mosie Kit.

The tertiary hypothesis for this study dives further into the primary hypothesis by breaking out the participants into groups based on their type of relationship and the source of their infertility to examine their cohort specific pregnancy rates.

Tertiary Hypothesis 1: There will be higher pregnancy rates when using the Mosie Kit when the source of infertility is male-based than when infertility is female-based.

Tertiary Hypothesis 2: There is a difference in pregnancy rates of people or couples with known fertility issues depending on the source of their infertility. Specifically, the following sources of infertility will be examined if sufficient data is available.

- o PCOS
- Endometriosis
- Low AMH or low ovarian reserve
- Low sperm count
- Sperm motility issues
- Unexplained infertility
- Erectile dysfunction
- Performance issues or sexual anxiety, or inability to orgasm with partner.
- Vaginismus or vulvodynia
- Tilted uterus
- Multiple uterus/cervix
- Loss of a fallopian tube

Tertiary Hypothesis 3: There will be a difference between individuals who perform 2 insemination instances as described in the instructions and those that follow a different schedule or dosage number.

Additionally since we are in the midst of a pandemic with COVID-19, exploratory analysis will be conducted on the stress levels and its impact on family expansion plans.

Tertiary Hypothesis 4: COVID-19 has affected people's family expansion plans.

Tertiary Hypothesis 5: There will be a decrease in pregnancy rates in those using the Mosie Kit during the Months of March - June.

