Appendix A: Online Survey Tool and Consent Form (Google Form)

This section shows what the Google Form will look like to the study participant. These are the questions the participant will be asked.

The first page of the study contains the consent form and the question that confirms the participant's agreement to participate.

There is skip logic for certain sections. For example, if the participant selects one cycle of using Mosie, the information related to cycles 2-6 will be skipped. If the participant selects that she is pregnant the questions related to the pregnancy will be asked, otherwise they will be skipped. If a donor was used, the questions related to producing a sperm sample will be skipped.

Note: Final language and questions might be tweaked or revised at any time to increase clarity.

MOSIE-001 © 2020 Mosie Baby Page 38

[figure not shown]
This is the inclusion/exclusion form.

If Participant selected to not participate in the study, he/she will see this screen next. If the participant said he/she is not 18 or older or has not used Mosie this screen will be displayed.

[figure not shown]

Qualifying participants will continue the survey on this page.

[figure not shown]

[figure not shown]
	ch of these diagnoses or issues do you believe are contributing to your rtility? *
	Not applicable
	PCOS
	Endometriosis
	Low AMH or low ovarian reserve
	Low Sperm count
	Sperm motility issues
	Erectile Dysfunction
	Performance issues or sexual anxiety, or inability to orgasm with partner
	Vaginismus or vulvodynia
	Tilted Uterus
	Multiple uterus/cervix
	Unexplained infertility
	Have only one functioning fallopian tube
П	Other:

[figure not shown]
No other method	is attempted			
Male/Female into	ercourse			
IVI or syringe oth	ner than Mosie			
IUI				
Femara				
Clomid				
IVF				
Cervical Cap				
Other:				
	None	1	2	3 or more
How many pregnancies have you had?	0	0	0	0
pregnancies	0	0	0	0
pregnancies have you had? How many live births have you had? How many pregnancies have you had that were	0	0	0	0
pregnancies have you had? How many live births have you had? How many pregnancies have you had	0	0	0	0

[figure not shown]

[figure not shown]
	0	1	2	3+
24-48 hours prior to ovulation	0	0	0	0
within 24 hours of ovulation	0	0	0	0
24-48 hours after ovulation	0	0	0	0
48+ hours after ovulation	0	0	0	0
Did you use Mosie fo Yes No	or another cy	cle?		

[figure not shown]

[figure not shown]

[figure not shown]

[figure not shown]

Mosie Kit Survey

* Required

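### Secondary Hypothesis 3 is about participants, but its planned measure is attempts over pooled cycles, with no participant-level result and no method for repeated cycles

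*Combined protocol and SAP*

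**What the plan says.** Sections 4.1 and 9.1 both word Secondary Hypothesis 3 about people. Section 9.1 has "The participants reported they used the kit as intended, specifically, using it within 24 hours of initial signs of ovulation". The sentence goes on to require a second use, in a later window following ovulation. Two timed uses are therefore part of the claim.

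The analysis under that hypothesis changes the unit: "Frequency rates related to timing of insemination at all reported cycles will be analyzed". Results are to be given as counts and as a "percentage of attempts at each time point in comparison with total cycles where the Mosie Kit was used. T-tests will also be used". What the t-tests compare, and on which unit, is not stated.

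Appendix A shows that cycles repeat within a person: "if the participant selects one cycle of using Mosie, the information related to cycles 2-6 will be skipped". The timing grid shown there records 0, 1, 2 or 3+ attempts in each window, and is followed by a question on whether the kit was used for another cycle.

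Section 9.4.1 refers back to section 9.1 for the analysis of each hypothesis. Its only fallback is a transformation or a non-parametric test. Section 9.2 computes precision on completed surveys, that is, on participants.

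**The concern.** The hypothesis asks what share of participants used the kit at both intended times. The planned statistic answers a different question, in three ways.

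- Attempts divided by cycles is not a share of anyone, because one cycle can hold several attempts in one window.
- Separate totals for each window cannot show whether the same person met both windows in the same cycle.
- A person with six cycles counts six times as much as a person with one. People who conceive can be expected to stop, so those who have not conceived tend to count more. Section 6.2 itself allows that timing may affect pregnancy. If it does, well-timed users log fewer cycles and are under-represented.

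A further problem arises if the t-tests or any interval take the cycle as the unit. One person's cycles probably resemble each other, and nothing in the plan allows for that.

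Section 2.3.2 intends the results to show whether the kit's instructions are clear or need changing, so a figure that can be read as the share of compliant users should be that share.

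**Working it through.** **1. The plan's own precision (section 9.2).** Half-width = 1.96 × √(0.25/n). For n = 500 this is 4.4 points, and for n = 384 it is 5.0 points. Both stated figures reproduce, and both rest on one observation per participant.

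**2. What the planned ratio can and cannot show (constructed examples).**
- Three users report one cycle each. One makes three attempts in a window and two make none. Attempts over cycles = 3/3 = 100%, but 1 of 3 participants (33%) used that window.
- Two users report one cycle each. If A uses only the first window and B only the second, each window shows 1/2 = 50%. If A uses both and B neither, each window again shows 50%. The share meeting both windows is 0 of 2 in the first case and 1 of 2 in the second. The planned table cannot tell them apart.

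**3. How unequal the weights are.** Inputs are a per-cycle conception rate p of 10-15% (the figure for ICI/IVI in section 2.2) and at most six cycles (Appendix A). The probability of stopping after a failed cycle is an assumption, because the documents give none. With no early stopping, mean cycles = (1 − (1 − p)^6)/p, and the share never conceiving = (1 − p)^6.

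| p | Stopping after each failed cycle | Non-conceivers, % of participants | Non-conceivers, % of cycles | Ratio |
|---|---|---|---|---|
| 10% | none | 53 | 68 | 1.28 |
| 15% | none | 38 | 55 | 1.44 |
| 10% | 20% | 69 | 74 | 1.07 |
| 15% | 20% | 58 | 63 | 1.09 |
| 10% | 40% | 79 | 80 | 1.01 |
| 15% | 40% | 70 | 71 | 1.02 |

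**4. Effect on an on-time percentage.** Assume that half of 500 users always time correctly and half never do, so the true participant share is 50%. For simplicity this treats each cycle as on time or not.
- 15% vs 10% conception, up to six cycles, no stopping: mean cycles 4.15 and 4.69; pooled share 4.15/(4.15 + 4.69) = 47%.
- The same with 20% stopping after each failed cycle: 47.8%.
- The same rates with at most three cycles, no stopping: 2.57/(2.57 + 2.71) = 49%.
- 20% vs 5%, six cycles, no stopping: 3.69/(3.69 + 5.30) = 41%.
- 20% vs 5%, at most three cycles: 46%.

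**5. Effect on tests and intervals if the cycle is the unit.** Design effect = 1 + (m_w − 1) × ICC, where m_w = Σm²/Σm is the size-weighted mean number of cycles. Actual two-sided alpha = 2 × (1 − Φ(1.96/√design effect)). The ICC is assumed.
- Six cycles, no stopping: m_w = 5.39 at p = 10% and 5.07 at p = 15%.
- ICC 0.3: 1 + 4.39 × 0.3 = 2.32 and 1 + 4.07 × 0.3 = 2.22, so alpha is about 20% and 19%.
- ICC 0.1: design effect about 1.4, alpha about 10%.
- ICC 0.3 with 20% stopping: design effect 1.9-2.0, alpha 15-16%.
- ICC 0, or one cycle each: no inflation.

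At p = 10% with no stopping, 500 users give about 500 × 4.69 ≈ 2,340 cycles and an apparent half-width of ±2.0 points. At ICC 0.3 this becomes 2.02 × √2.32 ≈ ±3.1.

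**The case against.** A reader might infer that the plan treats cycles as independent. It does not say so. The t-test's unit, comparison and variance method are all missing, and a participant-level t-test would fit the text equally well. The firm finding is an omission. The inflation in step 5 applies only to a test or interval that uses cycles as the unit; it does not touch the descriptive counts and percentages that make up most of this analysis.

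A reader might also infer that unsuccessful users dominate the result. At 10-15% per cycle they hold most of the cycles, but mainly because they are usually most of the participants already. The extra weight is 1.28 to 1.44 times only if everyone continues to conception or six cycles. Purchases date from 2 to 8 months before the study, and section 2.3.2 describes each kit as supplying syringes for two inseminations in a cycle, so many people will log fewer. The 41% figure also needs a 20% vs 5% split, outside the 10-15% range in section 2.2, and completely fixed habits.

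Nor do the documents support saying that the interval must miss the true value. In step 4 at 15% vs 10%, a cycle-level interval misses 50% with six cycles and no stopping (47.0 ± 2.1). It includes 50% with at most three cycles (46.0 to 51.4) and with 20% stopping (47.8 ± 2.6). The hypothesis has no threshold, so there is no formal decision to reverse.

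Finally, per-cycle frequency is a legitimate description of use, and sections 6.4 and 10.1.8 foresee judging whether the intended use was followed, the latter for the person. Neither supplies an analysis for this hypothesis. These points limit the size and wording of the concern; the unit mismatch stands.

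**Conclusion.** The concern holds as a mismatch between hypothesis and measure. Followed as written, section 9.1 yields a cycle-weighted ratio that does not estimate the share of participants who met both windows, and neither it nor section 9.4 says how repeated cycles are handled. That much needs no assumption.

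The numerical consequences do. The weighting shift is about 1 to 3 points at 15% vs 10% conception, which is smaller than the ±4.4 points in section 9.2. It reaches about 9 points only in the worst case, and is small if many stop early or if timing is unrelated to the number of cycles. The overconfidence of a cycle-level test can be material even where the weighting shift is modest, but it depends on the assumed ICC and on the cycle being used as the unit. The change is worth making before analysis, for a secondary and mainly descriptive hypothesis.

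**What to change.** Amend the analysis text for Secondary Hypothesis 3 in section 9.1:

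- Classify each reported cycle by whether both windows stated in the hypothesis were met. State which rows of the survey grid count for each window, because the grid is worded relative to ovulation and the first window relative to its initial signs.
- Report the percentage of participants meeting both windows in their first reported cycle, and separately in all their reported cycles, each with a participant-level 95% confidence interval.
- Keep attempts per time point and per cycle as description only.
- If cycle-level inference is kept, weight each cycle by 1/(number of cycles that person reported) and use participant-clustered standard errors.
- Drop t-tests that take attempts or cycles as the unit. For any t-test that remains, state what is compared and on which unit.

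No new data are needed, because each survey response holds all of that person's cycles. The cost is SAP wording and a wider interval: about ±4.4 points at 500 participants, in line with section 9.2, instead of an apparent ±2.0 from pooled cycles.
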